8.2.2. Total GAG, DS GAG, and HS GAG

Total GAG, DS GAG, and HS GAG (expressed as a ratio to creatinine) measured in urine will be assessed over time from Screening till Month 36/end of study visit or early termination visit if applicable. Descriptive statistics of the observed values and change from baseline values will be provided at the scheduled visits. A corresponding listing and summary table will be provided.

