### **4.2 Exclusion Criteria**

Subjects who meet any of the following criteria will be excluded from participating in the study:

1. Known to be unresponsive to ERT.
2. Neutralizing antibodies in serum (immune response) to AAV2/6.
3. Serious intercurrent illness or clinically significant organic disease (unless secondary to MPS I) such as cardiovascular, hepatic, pulmonary, neurologic, or renal disease.
4. Receiving antiviral therapy for hepatitis B or C, or with active hepatitis B (HBV DNA positive or HBV surface antigen positive) or hepatitis C (HCV RNA viral load) or human immunodeficiency virus (HIV)-1/2 (HIV RNA viral load or HIV antibody positive); to be considered negative for hepatitis C after treatment of an active HCV infection, viral assays in 2 samples collected at least 6 months apart must be negative.
5. Lack of tolerance to ERT with significant infusion-associated reactions (IARs) or occurrence of anaphylaxis.
6. Polymorphisms in the ZFN-targeted region of the albumin locus.
7. Liver fibrosis score of 3 or 4 on a 0 to 4 point scale ([Desmet et al. 1994](#)) if subject has had a liver biopsy within 2 years of Screening.
8. Markers of hepatic dysfunction as evidenced by one or more of the following:
  - a. Platelet count  $<100,000/\mu\text{L}$

- b. Albumin  $\leq 3.2$  g/dL
- c. Total bilirubin  $> 1.5 \times$  upper limit of normal (ULN) and direct bilirubin  $\geq 0.5$  mg/dL
- d. Alkaline phosphatase  $> 2.0 \times$  ULN
- e. ALT or AST  $> 2.0 \times$  ULN

9. Creatinine  $\geq 1.5$  mg/dL.
10. Weight  $< 20$  kg at Screening.
11. Pregnant or breastfeeding female.
12. Contraindication to the use of corticosteroids.
13. Current treatment with systemic (IV or oral) immunomodulatory agent or steroid use (topical treatment allowed, e.g., for asthma or eczema).
14. History of active malignancy in past 5 years (non-melanoma skin cancer or cervical cancer *in situ* permitted).
15. Participation in prior investigational drug or medical device study within the previous 3 months.
16. Prior treatment with a gene therapy product.
17. History of alcohol or substance abuse that in the opinion of the Principal Investigator may interfere with study compliance.
18. History of therapeutic non-adherence.
19. Elevated or abnormal circulating  $\alpha$ -fetoprotein (AFP).
20. Any other reason that, in the opinion of the Principal Investigator or Medical Monitor, would render the subject unsuitable for participation in the study.

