3.4. Dose Modifications

No dose modifications are possible within an individual subject since this is a single infusion study.

4. General Statistical Considerations

Study days will be numbered relative to the date of SB-318 infusion. For assessments on or after the date of SB-318 infusion, the study day of events from SB-318 infusion is calculated as the date of event minus the date of infusion. For assessments prior to the date of SB-318 infusion, the study day of events from SB-318 infusion is calculated as the date of event minus the date of infusion. Thus, the study day of event before the date of the infusion will be negative number, and the study day of the date of infusion will be 0.

Baseline is defined as the last non-missing measurement prior to the SB-318 infusion. Where only date is available, the date of the collection must be prior to the date of SB-318 infusion. Where time is also available, the time of the collection must be prior to the time

of SB-318 infusion. For example, for vital signs parameters, measures that are taken at the latest time prior to the infusion will be defined as baseline values. Measurements that are obtained after infusion will be considered as post-baseline values. If the measurement of a variable is not made on a given subject prior to infusion, then that subject will be considered not to have a baseline value for that variable. Change from baseline is defined as post-baseline assessment minus baseline assessment.

Continuous data will be summarized using the following descriptive statistics: number of subjects (n), mean, standard deviation (SD), median, minimum and maximum, where appropriate. Categorical data will be summarized using the frequency count (n) and percentage (%) of subjects for each category, where appropriate.

Unless specified otherwise, all the summary tables will be presented by treatment cohort and overall, and all the collected data will be presented in the listings, and data displayed in the listings will be sorted by treatment cohort and subject identifier.

No imputation will be applied for missing data unless otherwise specified.

All analyses will be conducted using SAS® Version 9.3 or later. The Medical Dictionary for Regulatory Activities (MedDRA 23.0) will be used for coding adverse events.

Concomitant medication data will be coded using the World Health Organization (WHO) Drug Dictionary.

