4.1. Sample Size

This study will enroll up to 27 subjects (1 subject in Cohort 2 and 2 subjects in each of the other 6 cohorts with potential enrollment of approximately 2 additional subjects in any cohort).

The sample size for this study was not based on statistical considerations, but is considered sufficient to provide preliminary assessments of the safety and tolerability of SB-318 in subjects with MPS I, as well as biochemical changes related to the pathophysiology of MPS I. Subjects who prematurely discontinue the study prior to the 12 months of study follow-up (i.e., subjects who were enrolled but not dosed, were lost to follow-up, or discontinued prematurely for another reason) may be replaced at the discretion of Sangamo.

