8.2.4. AAV2/6 clearance in plasma, saliva, urine, stool, and semen

Presence and shedding of AAV2/6 vector DNA, by PCR in plasma, saliva, urine, stool and semen (males only) will be conducted over time from Baseline till Week 48. The level of vector genome from each type of sample will be summarized by visit. A corresponding listing and summary table will be provided.

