Prog Notes: Post-baseline visits to be summarized include Weeks 4, 8, 12, 16, 20, 24, 28, 32, 36, 40, 44, 48, 52, Months 15, 18, 21, 24, 27, 30, 33, 36/EOS, or Early Termination Visit if applicable. Repeat for parameters in the following PARAMCD order: CREAT, MM1DR, MM1DU, MM1HR, and MM1HU.

Table 14.2.3
Change from Baseline in AAV2/6 Clearance
Safety Set

Parameter: AAV2/6-hIDUA (Copies/10 ul Plasma)

Visit	SB-318 1.00E+13 vg/kg (N=xx)		SB-318 5.00E+13 vg/kg (N=xx)		Total (N=xx)	
	Actual Value	Change From Baseline [1]	Actual Value	Change From Baseline [1]	Actual Value	Change From Baseline [1]
BASELINE						
n	xx		xx		xx	
MEAN (SD)	xx.x (xx.xx)		xx.x (xx.xx)		xx.x (xx.xx)	
MEDIAN	xx.x		xx.x		xx.x	
MIN, MAX	xx, xx		xx, xx		xx, xx	
VISIT X						
n	xx	xx	xx	xx	xx	xx
MEAN (SD)	xx.x (xx.xx)	xx.x (xx.xx)	xx.x (xx.xx)	xx.x (xx.xx)	xx.x (xx.xx)	xx.x (xx.xx)
MEDIAN	xx.x	xx.x	xx.x	xx.x	xx.x	xx.x
MIN, MAX	xx, xx	xx, xx	xx, xx	xx, xx	xx, xx	xx, xx

..
Note: Baseline is defined as last non-missing measurement prior to dosing.

[1]Change from baseline: post-baseline value - baseline value. For the change from baseline, only subjects with a value at both baseline visit and the specific post-baseline visit are included.

Source Data: Listing 16.2.9.6.1

<DIRECTORY PATH>PROGRAM NAME Executed: DDMMYYYY hh:mm

Prog Notes:

1. Please repeat for test AAV2/6-ZFN 47171 and other specimen (Saliva, Urine, Stool and Semen (Males Only)).
2. Post-baseline visit to be summarized include Day 7, Weeks 2, 4, 8, 12, 16, 20, 24, 36, 48.
3. Display visit Day 1 (12hr post-infusion) for Plasma only.

Table 14.2.4
Change from Baseline in Forced Vital Capacity (FVC)
Safety Set

Parameter: FVC (%)

Visit	SB-318 1.00E+13 vg/kg (N=xx)		SB-318 5.00E+13 vg/kg (N=xx)		Total (N=xx)	
	Actual Value	Change From Baseline [1]	Actual Value	Change From Baseline [1]	Actual Value	Change From Baseline [1]
BASELINE						
n	xx		xx		xx	
MEAN (SD)	xx.x (xx.xx)		xx.x (xx.xx)		xx.x (xx.xx)	
MEDIAN	xx.x		xx.x		xx.x	
MIN, MAX	xx, xx		xx, xx		xx, xx	
VISIT X						
n	xx	xx	xx	xx	xx	xx
MEAN (SD)	xx.x (xx.xx)	xx.x (xx.xx)	xx.x (xx.xx)	xx.x (xx.xx)	xx.x (xx.xx)	xx.x (xx.xx)
MEDIAN	xx.x	xx.x	xx.x	xx.x	xx.x	xx.x
MIN, MAX	xx, xx	xx, xx	xx, xx	xx, xx	xx, xx	xx, xx

...
Note: Baseline is defined as last non-missing measurement prior to dosing.

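### Urine GAG and vector copies are summarised only as raw values and absolute differences; the vector change column adds nothing to the observed value, and the mean GAG change is weighted to the highest baseline.

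*SAP*

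**What the plan says.** SAP Section 4 sets one list of statistics for all continuous data (n, mean, SD, median, minimum, maximum). It takes baseline as the last non-missing value before infusion and states: "Change from baseline is defined as post-baseline assessment minus baseline assessment".

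- **Urine GAG.** SAP 8.2.2 states that "Descriptive statistics of the observed values and change from baseline values will be provided at the scheduled visits". The shell for Table 14.2.2 applies this to total GAG in mg/mmol creatinine and repeats it for the other urine parameters.
- **Vector.** SAP 8.2.4 says only that "The level of vector genome from each type of sample will be summarized by visit". The change column comes from the shell for Table 14.2.3, titled "Change from Baseline in AAV2/6 Clearance", which uses raw copies (per 10 ul for plasma).

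Neither endpoint has a percent change, ratio, log scale or geometric mean. The SAP gives no rule for undetectable PCR results, and neither SAP 8.2.4 nor the shell counts subjects who are negative or cleared. Both shells have three columns: 1.00E+13, 5.00E+13 and Total.

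Two further provisions matter. Protocol 4.2 excludes "Prior treatment with a gene therapy product". Protocol 9.21 collects each specimen type until three consecutive results are negative or undetectable, and SAP Section 4 imputes nothing unless otherwise specified.

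**The concern.** Both quantities are naturally read as ratios: a GAG/creatinine level that halves or doubles, and a copy number that may fall through several orders of magnitude. An arithmetic mean of raw values or differences gives most weight to whoever is highest.

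For vector there is a second problem. The endpoint is clearance, meaning loss of vector after dosing, but the reference point for change is a sample taken before any vector was given. The event the protocol acts on, three consecutive negatives, is not tabulated. These rows are the planned summaries of two secondary endpoints, so a reader of the tables could misjudge the proportional GAG response and could not read off clearance.

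**Working it through.** **1. Cohort size.** SAP 4.1 states "This study will enroll up to 27 subjects (1 subject in Cohort 2 and 2 subjects in each of the other 6 cohorts". It then allows each cohort to grow by about two.
- Base: 1 + 6 x 2 = 13. Expansion: 7 x 2 = 14. Total: 13 + 14 = 27, which reproduces the stated maximum.
- SAP 4.1 names Cohort 2 as the single-subject cohort, while the cohort tables name Cohort 1. The total is the same.
- There is no power figure to check: "The sample size for this study was not based on statistical considerations".
- A cohort therefore holds 1 or 2 subjects, or about 3 or 4 if expanded. At n of 2 or fewer the median equals the mean and gives no protection.

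**2. Vector change column.** Change = post-infusion value - pre-infusion value. With a pre-infusion value of 0, change = post-infusion value at every visit. If undetectable is stored as text, the difference cannot be computed and the column is empty.

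**3. Raw vector means, n=2 (assumed copies).** Top share = higher value / sum; geometric mean = square root of the product.

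| Copies | Arithmetic mean | Geometric mean | Top share |
|---|---|---|---|
| 1E6, 1E3 | 500,500 | 31,623 | 99.9% |
| 1E5, 1E4 | 55,000 | 31,623 | 90.9% |
| 2E5, 1E5 | 150,000 | 141,421 | 66.7% |

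The spread drives the result: at 2-fold the two means nearly agree.

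**4. Later visits.** Take one subject who has had three negatives and is no longer sampled, and one still at 1E4 (assumed). The table prints n=1 and mean 10,000. Counting the cleared subject at 0 would give (0 + 10,000)/2 = 5,000. The printed mean describes the remaining shedder only.

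**5. Urine GAG, n=2 (assumed baselines).** One subject falls 30% and the other rises 50%. On the ratio scale the answer never moves: mean percent change = (-30 + 50)/2 = +10%, and geometric mean ratio = sqrt(0.7 x 1.5) = 1.025.

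| Baselines (faller, riser) | Changes | Mean absolute change |
|---|---|---|
| 100, 20 | -30, +10 | -10.0 |
| 60, 30 | -18, +15 | -1.5 |
| 40, 40 | -12, +20 | +4.0 |

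The mean turns negative when 0.3 x (faller's baseline) exceeds 0.5 x (riser's baseline), that is, at a baseline ratio above 0.5/0.3 = 1.67.

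The absolute scale also hides agreement. If baselines of 30 and 120 both halve, the changes are -15 and -60 (mean -37.5, SD 31.8), although each subject fell exactly 50%.

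**6. How often signs differ.** Two-subject pairs were simulated with normal log baselines (SD 0.3 to 1.0) and normal log responses centred on no change (SD 0.2 to 0.4). Among pairs responding in opposite directions, the mean absolute change was negative with a geometric mean ratio above 1 in about 2% to 11%. The two scales disagreed in sign, either way, in about 11% to 26%. These SDs are assumptions.

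**The case against.** The strongest reply is that the tables already show what matters. At n=2 the minimum and maximum are the two subjects' changes. If one subject goes from 30 to 60 and another from 120 to 60, the cell prints mean -15.0, SD 63.6, minimum -60 and maximum 30, so the opposite directions are plain. Listings 16.2.9.4 and 16.2.9.6.1 give every result. SAP Section 1 rules out hypothesis testing, and Protocol 13.5 itself specifies actual value and change for urine GAG. Absolute values can also be read against the normal range in the listing (0 to 24 for total GAG).

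Most of this stands. It makes the GAG effect modest and is a reason to keep the existing columns. It is weaker for an expanded cohort or the Total column, where minimum and maximum show only two subjects. The listings carry no change column. The plots over time by cohort in Protocol 13.5 would help, but SAP 8.2 does not carry them and no figure shell is listed.

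It is also fair that a floor for undetectable results is a new choice that matters at n=2. One subject at 1E6 and one undetectable give a geometric mean of sqrt(1E6 x 1) = 1,000 at floor 1 and sqrt(1E6 x 10) = 3,162 at floor 10.

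Three stronger readings are tempting, and the documents do not support them:
- **That the Total column pools doses 12-fold apart, so the top dose dominates.** SAP 3.1 lists a 1.20E+14 cohort, but the shells have only 1.00E+13 and 5.00E+13 columns, 5-fold apart.
- **That apparent clearance in one subject could mask rising vector in another.** An example moving from 1E6 and 1E2 to 1E4 and 1E4 needs a 100-fold rise after a single infusion of vectors that Protocol 8.1 describes as non-replicating. The minimum would show it in any case.
- **That the vector change column carries no information at all.** If pre-dose samples are negative it repeats the observed value, which is redundant rather than wrong.

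**Conclusion.** The point holds as an inexpensive improvement to two tables. It does not show that the planned results would be wrong.

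The vector part is the firmer one. Given negative pre-dose samples, which the exclusion makes likely but does not prove, the change column adds nothing beyond the observed value and cannot describe clearance. A 10- to 1000-fold spread puts 91% to 99.9% of the sum on one of two subjects, and stopping collection after three negatives leaves later means to those still shedding.

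The GAG part is conditional and modest. It needs unequal baselines, and the documents give no spread. A single-subject cohort is unaffected, and at n=2 the minimum, maximum and listings reveal opposite responses. All GAG and copy values used here are illustrative.

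**What to change.** - **Table 14.2.2 and SAP 8.2.2:** keep the existing columns and add percent change and geometric mean ratio to baseline for total GAG, DS and HS.
- **Table 14.2.3 and SAP 8.2.4:** replace change from the pre-infusion value by log10 copies (geometric mean) per visit and log10 change from each subject's first post-infusion sample (12-hour plasma; Day 7 for other specimens). Both samples are already collected and in the shell.
- **Undetectable results:** state one floor value, in the unit of each specimen type, and show how many subjects sit at it.
- **Clearance:** at each visit give the number negative and the number who have met three consecutive negatives, keeping cleared subjects in the denominator after their sampling stops. This is what deals with the later-visit problem; a log scale alone would not.
- **Pooling:** present vector results by dose, without the Total column.

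The cost is wording in two SAP sections, two revised shells with extra columns, and one chosen floor value, to which the geometric mean is sensitive at n=2. The counts do not depend on that choice. No new data are needed.

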8.2.3. ERT Administration and Withdrawal

ERT withdrawal may occur at any time after the Week 12 visit. ERT withdrawal may be repeated if it was found to be unsuccessful previously. Concomitant medications, adverse events, liver panels, GAG, and IDUA testing will be done at each ERT withdrawal monitoring visit. These will be displayed in the relevant listings.

Frequency of ERT administration will be summarized by the following timepoints:

- Prior to first dose of infusion
- Within the first 30 days of infusion
- After the first 30 days of infusion

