### **6.1 Screening**

The objective of Screening is to identify subjects who meet the stated inclusion and exclusion criteria and who are willing and able to participate in the study. Screening may take up to approximately 3 months and may be performed across several visits.

The following assessments and procedures will be performed:

- Obtain a signed and dated subject informed consent form and authorization document to use and disclose medical information prior to performing any study-specific procedures.
- Obtain a complete medical history.
- Review and record concomitant medications.
- Review the inclusion and exclusion criteria.
- Collect demographic information.
- Assign a subject number.
- Physical examination.
- Vital signs.
- Assessment of AEs.
- ERT administration log.
- 12-lead electrocardiogram (ECG).
- Echocardiogram (ECHO).
- Chest x-ray.
- Pregnancy test (for females of childbearing potential only).
- Clinical laboratory tests.
- Liver panel.
- MPS I gene sequencing.
- SNP analysis.
- Viral load.
- Neutralizing antibodies to AAV2/6.

- GAG testing in urine (collect samples on 3 separate days, each collection occurring at least 7 days after the previous, and all collections occurring at least 7 days after ERT administration [+/-1 day] but prior to the next ERT infusion).
- IDUA / GAG testing in blood (collect 7 days after ERT administration [+/-1 day]).
- Circulating AFP level.
- Pulmonary function tests (PFTs).
- VABS-II (Vineland Adaptive Behavior Scales) test.
- Neurocognitive abilities assessment.
- MRI of liver.

Subjects may be re-screened for participation in the study in the judgement of the Principal Investigator and after consultation with Sangamo. For re-screening, the following assessments performed in the previous 6 months may be used for evaluation of inclusion/exclusion criteria at the judgement of the Principal Investigator:

- ECHO.
- Chest X-Ray.
- PFTs.
- MRI of liver and/or brain and cervical spine.

Further, genetic marker analysis including SNP analysis and MPS I sequencing will not be repeated as results of these assessments do not change over time.

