#### **6.11 ERT Withdrawal (any time after Week 12)**

Subjects who are willing and who are at least 12 weeks post administration of SB-318 may be considered for withdrawal of ERT by the Principal Investigator after consultation with the Sponsor. If undergoing ERT withdrawal, subjects must be medically stable and agree to increased safety monitoring and laboratory testing until the ERT Withdrawal Follow-Up visit.

The ERT Withdrawal visit may occur concurrently or independent of a regular scheduled visit.

The ERT Withdrawal visit should be combined with a regular scheduled visit whenever possible to reduce study burden.

The following assessments and procedures will be performed:

- Review and record concomitant medications.
- Physical examination.
- Vital signs.
- Assessment of AEs.
- ERT administration log.
- Clinical laboratory tests.
- Liver panel.
- GAG testing in urine.
- IDUA / GAG testing in blood.
- PFTs.
- 6MWT.

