### 13.5 Secondary Endpoints

The following are secondary endpoints for this study:

- Change from Baseline in:
  - IDUA activity measured in blood.
  - Total GAG, DS GAG, and HS GAG levels (expressed as ratio to creatinine) measured in urine.
  - Monthly and annualized frequency and dose of Aldurazyme (or equivalent ERT).
- AAV2/6 clearance measured by vector genomes in plasma, saliva, urine, stool, and semen by PCR.

At each sampling time point, the actual value and the change from baseline for IDUA activity and GAG levels in urine will be summarized using descriptive statistics and plotted over time by treatment cohort.

For subjects who undergo ERT withdrawal, changes from pre- to post- ERT withdrawal in the frequency and dose of ERT infusions will be evaluated and summarized using monthly, quarterly, and annualized total dose and number of infusions. Duration of ERT withdrawal may also be analyzed.

AAV2/6 clearance measured by vector genomes in the different samples will be plotted over time by treatment cohort.

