3.2.2. Secondary Endpoints

The following are secondary endpoints of this study:

1. Change from baseline over time in the following assessments:
 - IDUA activity measured in blood.
 - Total GAG, DS GAG, and HS GAG (expressed as a ratio to creatinine) measured in urine.
 - Monthly and annualized frequency and dose of Aldurazyme (or equivalent ERT).
2. AAV2/6 clearance measured by vector genomes in plasma, saliva, urine, stool, and semen by polymerase chain reaction (PCR).

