8.2. Secondary Endpoint Analysis

The secondary analysis is to evaluate change from baseline over time for the endpoints mentioned in Section 3.2.2.

At each sampling time point, the actual value and the change from baseline for IDUA activity and GAG levels in urine will be summarized using descriptive statistics by treatment cohort.

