9.3. Pregnancy Test

Urine pregnancy test will be conducted for females of childbearing potential at Screening and Baseline, at Day 0 if >7 days from Baseline. It will be performed until Week 48 or until 3 consecutive plasma samples are negative for AAV2/6, whichever happens first. If urine pregnancy test result is positive, equivocal or impractical, a serum pregnancy test will be performed to confirm. The data will be presented in a listing.

10. Safety Monitoring Committee

An independent SMC composed of appropriate medical and scientific expertise will provide oversight of the study. For the cohort safety review, the SMC will be convened after the completion of each cohort (at least four weeks after the last subject within that cohort has received the study drug) to determine if it is safe to escalate to the next dose cohort. For the rolling safety review, the SMC will meet to review all available safety data approximately every 4-6 months after the first Cohort Safety Review. These meetings may be combined with subsequent cohort safety review meetings as appropriate.

The SMC may be convened at any time if there are excessive or unexpected toxicities associated with the conduct of the protocol. Specifically, the SMC will be convened earlier if the following occurs:

- Any two Grade 2 AEs in the same SOC that last more than 2 weeks with treatment or any one Grade 3 or greater AE, if these AEs are not related to the primary MPS I disease or treatment of the MPS I disease.
- SAEs not related to the primary MPS I disease.
- Death of a subject.
- Development of a malignancy.

Data analyses for SMC review will be presented in a separate document.

When no further enrolling or dosing decisions are required of the SMC, the SMC will no longer meet. Sangamo will continue to review subject safety data on an ongoing basis.

11. Changes to the Statistical Analysis Section of the Protocol

Secondary endpoint, change of baseline over time of dose of Aldurazyme (or equivalent ERT), will no longer be summarized.

12. References

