Table 14.1.5
Concomitant Medications
Safety Set

Note: Patients may have more than one medication per ATC level 4 category and preferred term. At each level of patient summarization, a patient is counted once if the patient reported one or more medications. Concomitant medication is defined as any medication, including over-the-counter medicinal products, dietary supplements, herbal medications, and medications given in treatment of AEs, taken by a subject from Screening throughout the course of the study. Subjects who received ERT prior to study enrollment should continue to receive ERT as per standard of care, except during the week of the SB-318 infusion, and such treatment should be recorded as concomitant medication. Treatment with prednisone or equivalent corticosteroid and pre-treatment with acetaminophen and diphenhydramine hydrochloride should also be recorded as concomitant medication.

Concomitant medications were coded with the WHO Drug dictionary dated XXXXXX, 20XX.

ATC classes are sorted in decreasing order of frequency based on the total number subjects who take each medication in the total column. Preferred terms within each drug class are sorted alphabetically
Source Data: Listing 16.2.4.2, Listing 16.2.4.3

<DIRECTORY PATH>PROGRAM NAME Executed: DDMMYY YYYY hh:mm

Table 14.1.5
Concomitant Medications
Safety Set

ATC Level 4 Preferred Term	SB-318 1.00E+13 vg/kg (N=xxx) n (%)	SB-318 5.00E+13 vg/kg (N=xxx) n (%)	Total (N=xxx) n (%)
TOTAL NUMBER OF CONCOMITANT MEDICATIONS			
NUMBER OF PATIENTS WITH AT LEAST ONE CONCOMITANT MEDICATION	xx (xx.x)	xx (xx.x)	xx (xx.x)
ATC LEVEL 4 #1	xx (xx.x)	xx (xx.x)	xx (xx.x)
PREFERRED TERM #1	xx (xx.x)	xx (xx.x)	xx (xx.x)
PREFERRED TERM #2	xx (xx.x)	xx (xx.x)	xx (xx.x)
PREFERRED TERM #3	xx (xx.x)	xx (xx.x)	xx (xx.x)
PREFERRED TERM #4	xx (xx.x)	xx (xx.x)	xx (xx.x)

Notes are listed on page 1.

<DIRECTORY PATH>PROGRAM NAME Executed: DDMMYYYY hh:mm

Prog Note: Medications will be sorted in descending order by ATC level 4 category based on the total of all treatment groups. Within each ATC level 4 category, preferred terms will be sorted in decreasing order of frequency based on the total of all treatment groups.

Table 14.1.6
Summary of Enzyme Replacement Therapy Administration
Safety Set

Cohort	Subject ID	Number of ERT Administrations		
		Prior to First Dose of SB-318 Infusion	0 - 30 Days Post SB-318 Infusion	> 30 Days Post SB-318 Infusion
SB-318 1.00E+13 vg/kg	XXXXXX	XXX	XXX	XXX

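### The planned ERT table gives raw infusion counts in windows of unequal length, not the change in monthly and annualized ERT frequency that the SAP keeps as a secondary endpoint

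*SAP*

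**What the plan says.** SAP 3.2.2 lists, under change from baseline over time, "Monthly and annualized frequency and dose of Aldurazyme (or equivalent ERT". SAP 8.2 repeats the intent: "The secondary analysis is to evaluate change from baseline over time for the endpoints mentioned in Section 3.2.2".

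Protocol 13.5 specifies a further comparison for subjects who stop ERT: "changes from pre- to post- ERT withdrawal in the frequency and dose of ERT infusions will be evaluated". It asks for this on monthly, quarterly and annualized scales; the protocol synopsis mentions only the annualized scale.

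SAP 8.2.3 is the only section that deals with ERT use as an endpoint. It states "Frequency of ERT administration will be summarized by the following timepoints" and names three windows anchored on the SB-318 infusion: before it, within 30 days, and after 30 days. Table 14.1.6 in the SAP shells has one row per subject and, under the heading "Number of ERT Administrations", one cell per window. No other table shell reports ERT frequency. Table 14.1.5 covers ERT only as a concomitant medication.

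SAP section 11 declares one departure from the protocol analysis: "Secondary endpoint, change of baseline over time of dose of Aldurazyme (or equivalent ERT), will no longer be summarized". It says nothing about frequency.

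**The concern.** The SAP promises a rate and its change but plans a count. A count can stand in for a rate only if the windows have the same length for every subject and in every period. Here they do not.

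- **The prior window** starts when the ERT log starts, at Screening (protocol 9.34). On Screening, protocol 6.1 says "Screening may take up to approximately 3 months and may be performed across several visits". Baseline assessments may take up to 21 days before infusion.
- **The late window** has no fixed end. Follow-up is 36 months, but subjects may move to the long-term follow-up study from Month 12, or earlier case by case.
- **Withdrawal falls inside the late window.** Protocol 6.11 says "Subjects who are willing and who are at least 12 weeks post administration of SB-318 may be considered for withdrawal of ERT". For anyone who stops ERT, the late cell adds on-ERT time to off-ERT time, so the protocol 13.5 comparison cannot be read from it.

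The protocol and SAP both give removing or reducing the need for ERT as the purpose of SB-318, and this is the secondary endpoint that measures it directly. SAP section 11 announces the loss of dose alone, so a reader would expect frequency to be analysed as the protocol says.

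**Working it through.** The plan states no figure to reproduce. The check compares the texts and then counts infusions by window.

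**1. Endpoint against output**

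| Required | Source | In SAP 8.2.3 / Table 14.1.6? |
|---|---|---|
| Monthly and annualized frequency | SAP 3.2.2 | No; counts without days observed |
| Change from baseline | SAP 3.2.2, 8.2 | No |
| Pre- versus post-withdrawal frequency | Protocol 13.5 | No; no split at withdrawal |
| Dose | SAP 3.2.2, protocol 13.5 | No, but declared in SAP section 11 |

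SAP 8.2.1 and 8.2.2, on IDUA activity and urine GAG, both specify change from baseline; 8.2.3 does not. The general baseline definition in SAP section 4 is the last single measurement before infusion. That cannot supply a baseline rate, which needs a period.

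**2. Window lengths**

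- Prior: about 91 days (3 months), or up to 91 + 21 = 112 days.
- Days 0 to 30: 31 days.
- After day 30: 365 − 30 = 335 days with 12 months of follow-up, 730 − 30 = 700 with 24, and 1095 − 30 = 1065 with 36.

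**3. Counts for a subject whose ERT never changes**

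Weekly ERT is assumed, because the documents describe ERT as weekly. Counts run over all seven possible weekdays and vary by about 1.

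- Prior: 91/7 = 13 to 112/7 = 16.
- Days 0 to 30: 4–5 if the infusion omitted around SB-318 falls before Day 0, and 3–4 if it falls after.
- After day 30: 47–48 (12 months), 100 (24 months), 152–153 (36 months).

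The ratio of late to prior count runs from 48/16 = 3.0 to 152/13 = 11.7 with no change in ERT use. A shorter Screening makes it larger.

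**4. Ordering of subjects**

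Annualized rate = count ÷ days × 365.25.

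| Subject | Follow-up | Count after day 30 | Rate per year |
|---|---|---|---|
| Off ERT for one year, from day 168 | 36 months | about 100 (99–101) | 100/1065 × 365.25 = 34.3 |
| Unchanged | 12 months | 48 | 48/335 × 365.25 = 52.3 |
| Unchanged | 24 months | 100 | 100/700 × 365.25 = 52.2 |
| Unchanged | 36 months | 152 | 152/1065 × 365.25 = 52.1 |

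By count, the subject who spent a year off ERT looks like a heavier user than the unchanged subject who left at Month 12, and the same as the one who left at Month 24.

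Whole rows can also coincide. With a 91-day prior window, a subject who never stops and leaves at Month 12 shows 13 / 4 / 48. So does a subject who stops for good at day 364 and is followed for 36 months. The second subject's late-window rate is 48/1065 × 365.25 = 16.5 per year, and the post-withdrawal rate is 0.

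**5. Dividing the late cell by time is not enough**

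Withdrawal at Week 12 is day 84, so days 31 to 84 (54 days) precede even the earliest withdrawal and hold 7–8 infusions. A subject who stops for good at Week 12 has a post-withdrawal rate of 0. The late cell gives:

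- 12 months: 7/335 × 365.25 = 7.6 to 8/335 × 365.25 = 8.7 per year.
- 36 months: 7/1065 × 365.25 = 2.4 to 8/1065 × 365.25 = 2.7 per year.

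The same clinical course gives different figures depending only on follow-up.

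**The case against.** The strongest reply is that little is lost. The study is small and descriptive, with no hypothesis tests. Table 14.1.6 is already per subject, Listing 16.2.4.2 dates every infusion, and Listing 16.2.1.1 gives each completion or termination date. At equal follow-up a large fall in ERT use would still show in the counts. All of this is true and limits the harm. But a listing from which a reader could work out the endpoint is not a planned analysis of it, and unequal follow-up is built into the protocol.

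A second reply is that SAP 8.2.3 says frequency, not count, and that SAP 8.2 covers change from baseline in general. It is fair that the reduction to counts is made in the table shell. But neither section gives a baseline period, a denominator or an output for ERT.

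On the figures:

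- Protocol 9.34 itself says a standing weekly schedule should not be assumed. Weekly ERT is used here only for illustration; the unequal windows exist under any schedule.
- At the edges of the counts the ratios are 47/16 = 2.9 and 153/13 = 11.8. If the omitted infusion falls before Day 0, the prior count is 12 to 15 and the upper edge is 153/12 = 12.8.
- The mixing in the late cell affects only subjects who withdraw, which is optional. The 54 days shift by about a week if withdrawal is tied to the Week 12 visit with its one-week window.

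None of these changes the conclusion.

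**Conclusion.** The concern holds and should be fixed. As written, SAP 8.2.3 and Table 14.1.6 do not report the frequency endpoint that SAP 3.2.2 retains, and do not make the protocol 13.5 withdrawal comparison. The dose part was openly dropped; the loss of the frequency rates is undeclared.

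Under weekly ERT, unchanged use yields late counts roughly 3 to 12 times the prior count, and unequal follow-up can reverse or hide a real difference between subjects. These sizes rest on the weekly schedule, a prior window of 91 to 112 days and follow-up of 12 to 36 months. The mismatch between endpoint and output rests on the text alone. No data are lost.

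**What to change.** Rewrite SAP 8.2.3 and Table 14.1.6. For each subject and period, show infusions, days of observation, rate per month (30.4 days) and per year, and change from the pre-infusion rate. Suitable periods are:

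1. Screening to SB-318 infusion.
2. Infusion to the ERT Withdrawal visit, or end of follow-up.
3. ERT Withdrawal visit to resumption, or end of follow-up.
4. After resumption, with each repeat withdrawal as its own period.

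For subjects who withdraw, show pre- against post-withdrawal rates on the protocol 13.5 scales, including quarterly, or state why the synopsis scale is used instead. Show subjects not on ERT at entry separately. State in a footnote how the omitted infusion week enters the denominator.

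Take infusion dates from the ERT log, withdrawal from the visit record, resumption from the log and the ERT Clinical Assessment eCRF, and end of follow-up from disposition. If the rates are meant to be dropped, say so in SAP section 11.

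The cost is SAP wording, one table shell and a little programming. No new data are needed.
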